- For the second principal secondary endpoint, the LS means estimated from treatment difference, will be presented along with one-sided p-value and 95% CI. The number of participants contributing to the analysis and the associated mean and standard deviation of the baseline and Week 28 SF-36 Vitality sub-score value will also be displayed with the results of the model.
- For the second principal secondary endpoint, all available SF-36 vitality sub-score values (on-treatment) will be displayed graphically for each scheduled study Week 8, Week 12, and Week 28 visit using a line plot.
- For the second principal secondary endpoint, all available SF-36 vitality sub-score change from baseline values (on-treatment) will be displayed graphically for each scheduled study Week 8, Week 12, and Week 28 visit using a line plot. The line plot of mean values \pm standard errors by time will include horizontal reference line to identify zero change, and the number of participants by treatment group contributing to each mean value.
- SF-36 data will be summarized and analysed using both norm-based and traditional scoring, see Section 10.6.5 for details. The traditional scoring will be considered as the primary results and norm-based as supportive results.

Multiple Imputation HGB Increase ≥ 1.0 g/dL

- For the first secondary endpoint, the imputed data from the primary endpoint will be used for deriving the % of participants having a HGB increase of ≥ 1.0 g/dL from baseline to EP.

Multiple Imputation SF-36 Analysis

- For the SF-36 principle secondary endpoint, multiple imputation analysis will be performed using on treatment SF-36 values and conducted under a set of assumptions about missing sf-36 values (see Section 10.6.3).
 - Missing scheduled SF-36 data in both arms through Week 28 will be considered MAR and imputed using PROC MI procedure with NIMPUTE = 200 and FCS to generate 200 datasets. The seed for reproducibility is set to 205270. The imputations will be done by randomized treatment, include region as categorical covariate.
 - Week 28 SF-36 values will be computed and compared across treatment groups using the principle secondary ANCOVA model described above. Rubin's rules [Rubin, 1987]

CONFIDENTIAL

205270

- will be used to combine results of the imputed datasets using SAS PROC MIANALYZE procedure. As a result, a single estimated treatment difference and its standard error will be produced, with which a 95% CI will be calculated.

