- Subjects with scheduled off-treatment SF-36 data will be imputed assuming they were on treatment.
 - The low and high cutoffs at SF-36 values of 0 and 100 for traditional scoring and 22.89 and 70.42 for norm-based scoring will be applied to all imputed SF-36 values.
 - For the SF-36 principle secondary endpoint supportive analysis imputing subjects who have remote/over the phone SF-36 visits during Week 28 and those subjects who were treatment interrupted prior to their Week 28 visit will be performed using on treatment SF-36 values and conducted under a set of assumptions about missing sf-36 values (see Section 10.6.3). This is a similar imputation strategy as outlined above but will be based on on-treatment SF-36 values and consider those subjects who completed SF-36 remotely/over the phone or who were treatment interrupted prior to Week 28 as missing.

Supportive Analyses

- For the first principal secondary endpoint, a supportive analysis using while alive and on treatment strategy (on-drug analysis) will be performed using a Cochran-Mantel-Haenszel (CMH) chi-squared test, adjusting for treatment, and region (see Section 5.3), will be used to make comparisons between the treatment groups. No imputation will be performed for this analysis.
- For the second principal secondary endpoint, a treatment policy strategy (on and off treatment) analysis will be performed using an ANCOVA model including all participants with on and off treatment values, including factors for baseline score, treatment, and region. This will be done for both traditional and norm-based scoring. No imputation will be performed for this analysis.
- For the second principal secondary endpoint, a while alive and on treatment strategy (on treatment only) analysis will be performed using an ANCOVA model including all participants with on treatment values, excluding subjects who IP discontinue/rescue, including factors for baseline score, treatment, and region. This will be done for both traditional and norm-based scoring. No imputation will be performed for this analysis.

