| 
 • For the % of participants having an improvement in SF-36 Vitality Domain ≥ 6 from baseline at Week 28, a Cochran-Mantel-Haenszel (CMH) chi-squared test, adjusting for treatment and region (see Section 5.3), will be used to make comparisons between the treatment groups. This will be based on the traditional scoring. As in the second principal secondary endpoint, on-treatment SF-36 vitality sub-scores will be used, and exclude the measures taken after IP discontinuation. Subjects with missing SF-36 data will be imputed based on treatment status as described in Section 7.2.5.2. • Scoring for the SF-36 parameters and EQ-5D parameters is outlined in Section 10.6.5. • The mean change from baseline in SF-36 HRQoL scores (individual items of the Vitality Domain, overall score of the Physical Function Domain), EQ-5D-5L score, and EQ-VAS score will be analyzed using an MMRM approach with an unstructured covariance matrix to compare the difference in means between arms. The models will be fitted to HRQoL data collected after baseline up to Week 28, using on treatment values and exclude the measures taken after IP discontinuation. The model will include factors for treatment, time, region (See Section 5.3), treatment by time interaction, corresponding baseline value (HRQoL parameter or utility scores) and the baseline value by time interaction term. Analyses will be done with the MIXED procedure in SAS, using the Kenward-Roger option to estimate denominator degrees of freedom and standard errors. |
| Model Results Presentation |

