| 
NOT used currently)
 
 ▪ Tired/Low Energy/Weak domain: average items [CCI] (0-100 scale) ▪ Chest Pain/Shortness of Breath domain: average items [CCI] (0-100 scale) ▪ Cognitive domain: average items [CCI] (0-100 scale) ▪ [CCI] (0-100 scale) ▪ [CCI] (0-100 scale) ▪ [CCI] (0-100 scale) ▪ [CCI] (0-100 scale) |

| PGI-S |
|---|
| General Information & Scoring |
| 
 • The PGI-S is a 1-item questionnaire designed to assess a participant's impression of disease severity on a 5-point disease severity scale (absent, mild, moderate, severe, or very severe). • Scores range from [CCI] as follows: 
 ○ [CCI] ○ [CCI] ○ [CCI] ○ [CCI] ○ [CCI] |

| SF-36 |
|--|
| General Information & Scoring |
| 
 • The SF-36 acute version 2 is a 36-item generic quality of life instrument designed to measure a participant's level of performance in the following eight health domains: Physical Functioning, Role-Physical (role limitations caused by physical problems), Social Functioning, Bodily Pain, Mental Health, Role-Emotional (role limitations caused by emotional problems), Vitality, and General Perception of Health. • Scoring of the questionnaire data will be performed using Optum PRO CoRE scoring software version 1.4 using a traditional scoring and norm-based scoring approach using 2009 norms and the maximum data recovery mode to handle missing data. • The 8 domain scores and scores for the physical and mental component summary measures will be provided by the Optum PRO CoRE software. • For SF-36 question [CCI] full of life, and question [CCI] a lot of energy, will be transformed so the higher the score the better the health. The following formula will be used: 
 ○ $(5 - \text{aval}) + 1 = \text{transformed aval}$, where aval is raw score. ○ For example if a subject's answer is 4, a little of time, this will be transformed to a value of 2. |

| WPAI-ANS-CPV |
|--|
| General Information & Scoring |
| 
 • The WPAI-ANS-CPV is an anemia-specific questionnaire designed as a self-reported quantitative assessment of social functioning related to work and regular daily activities within two concepts: Work productivity impairments via absenteeism (time missed from work) and |

CONFIDENTIAL

205270

| WPAI-ANS-CPV |
|--|

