| 2.51. | ITT | EFF_T17 | Summary Statistics for On-Treatment SF-36 Individual Vitality Scores and 8 Domain Scores | On-treatment, both norm and traditional scoring needed for 8 domains and following individual vitality scores with PARAMCD="BP","BP_NBS","GH","GH_NBS","MH","MH_NBS","PF","PF_NBS","RE","RE_NBS","RP","RP_NBS","SF","SF_NBS","VT","VT_NBS","SF36423A","SF36427A","SF36429","SF36431" | DR, SAC |

CONFIDENTIAL

205270

| Efficacy: Tables | | | | | |
|------------------|------------|----------------------|--|---|-------------|
| No. | Population | IDSL / Example Shell | Title | Programming Notes | Deliverable |
| 2.52. | ITT | EFF_T18 | Summary Statistics for the Change from Baseline in On-Treatment SF-36 Individual Vitality Scores and 8 Domain Scores | On-treatment, both norm and traditional scoring needed for 8 domains and following individual vitality scores with PARAMCD="BP","BP_NBS","GH","GH_NBS","MH","MH_NBS","PF","PF_NBS","RE","RE_NBS","RP","RP_NBS","SF","SF_NBS","VT","VT_NBS","SF36423A","SF36427A","SF36429","SF36431" | DR, SAC |
| 2.53. | ITT | EFF_T19 | Summary of On-Treatment EQ-5D-5L Responses by Dimension and Visit | On-treatment | DR, SAC |
| 2.54. | ITT | EFF_T13 | Summary Statistics for On-Treatment EQ-5D-5L Scores | On-treatment | DR, SAC |
| 2.55. | ITT | EFF_T13 | Summary Statistics for On-Treatment EQ-VAS Scores | On-treatment | DR, SAC |
| 2.56. | ITT | EFF_T14 | Summary Statistics for the Change from Baseline in On-Treatment EQ-5D-5L Scores | On-treatment | DR, SAC |
| 2.57. | ITT | EFF_T14 | Summary Statistics for the Change from Baseline in On-Treatment EQ-VAS Scores | On-treatment | DR, SAC |
| 2.58. | ITT | EFF_T20 | Summary of Analysis of the Change from Baseline in On-Treatment SF-36 Individual Vitality Scores and Physical Function Domain Scores | On-treatment | DR, SAC |
| 2.59. | ITT | EFF_T15 | Summary of Analysis of the Change from Baseline in On-Treatment EQ-5D-5L Scores | On-treatment | DR, SAC |
| 2.60. | ITT | EFF_T15 | Summary of Analysis of the Change from Baseline in On-Treatment EQ-VAS Scores | On-treatment | DR, SAC |

CONFIDENTIAL

205270

| Efficacy: Tables | | | | | |
|---|------------|----------------------|--|---|-------------|
| No. | Population | IDSL / Example Shell | Title | Programming Notes | Deliverable |
| Secondary Efficacy Statistical Analyses: Work Productivity and Regular Daily Activity Impairment | | | | | |

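### The SF-36 Vitality responder cut of 6 points is a different criterion for observed scores, which move in steps of 6.25, than for imputed scores, which can take any value from 0 to 100

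*SAP*

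**What the plan says.** The SAP (Section 2.1, Table 1) adds a responder endpoint to the protocol's SF-36 analyses. Section 7.3.2.1 (HRQoL and Utility Score) introduces it: "For the % of participants having an improvement in SF-36 Vitality Domain ≥ 6 from baseline at Week 28", compared by a CMH test adjusting for region. On scale it says: "This will be based on the traditional scoring". Only on-treatment scores are used, and for the rest: "Subjects with missing SF-36 data will be imputed based on treatment status as described in Section 7.2.5.2".

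Section 7.2.5.2 says that missing scheduled scores are "imputed using PROC MI procedure with NIMPUTE = 200 and FCS to generate 200 datasets". The one restriction placed on the drawn values is a clip: "The low and high cutoffs at SF-36 values of 0 and 100 for traditional scoring". The type of FCS regression is not named, and neither rounding nor predictive mean matching is mentioned.

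Two other places fix the grain of the observed score. Section 10.6.5 reverses the positively worded items as (5 − score) + 1: "For example if a subject's answer is 4, a little of time, this will be transformed to a value of 2". Items therefore run from 1 to 5. The programming note for Table 2.51 in Section 10.10.6 asks for "both norm and traditional scoring needed for 8 domains and following individual vitality scores" and then lists four item codes.

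The output is the responder percentage in each arm, the relative response rate with its 95% CI, and a one-sided p-value compared with 0.025 for nominal significance (Section 7.3.2.1). Section 5.5 treats the additional secondary endpoints as exploratory and unadjusted.

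**The concern.** One numerical cut is applied to two kinds of number. A completed questionnaire cannot show a gain of 3, 4 or 5 points, because the smallest possible gain is 6.25, which is a response. A continuous imputed score can show a gain of 4 or 5, and that is a non-response. So a participant whose underlying improvement lies between half a step and 6 points may be classified differently according to whether the Week 28 score was observed or filled in.

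Two things are at stake: the responder percentage reported for each arm, which mixes the two criteria in proportion to the imputed share, and, to a lesser extent, the comparison between arms if those shares differ. They can differ because scores after treatment discontinuation are set aside and imputed, and meeting the rescue criteria requires stopping treatment (protocol Sections 7.7.2 and 8.1). The discrepancy does not need the missing-at-random model to be wrong.

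**Working it through.** **Inputs.** Four Vitality items (SAP 10.10.6, Table 2.51); five levels per item (SAP 10.6.5); score range 0–100 (SAP 7.2.5.2); SD 21 and effect 5 points for mean change in Vitality, 270 evaluable per arm (protocol 10.2.1); SD sensitivity range 19–23 (protocol 10.2.2). The protocol's SD is read as the SD of change.

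**The plan's own figure.** The documents give no figure for the responder endpoint, only for mean change. SE = 21 × √(2/270) = 1.807; 5/1.807 − 1.96 = 0.81; power = Φ(0.81) = 79%, as stated. The smallest significant difference is 1.96 × 1.807 = 3.54 (stated 3.5). The SD is therefore being read as the sponsor used it.

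**Step size.** 100 / (4 items × 4 increments) = 6.25.

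**Gap if the observed score is a normal variable rounded to the grid.** An observed gain of at least 6 is then a gain of at least half a step, 3.125, on the continuous scale. An unrounded imputed gain must reach 6. For mean change m:

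Gap = Φ((6 − m)/SD) − Φ((3.125 − m)/SD)

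| SD | m | Observed | Imputed | Gap (points) |
|---|---|---|---|---|
| 19 | 0 | 43.5% | 37.6% | 5.9 |
| 19 | 5 | 53.9% | 47.9% | 6.0 |
| 21 | 0 | 44.1% | 38.8% | 5.3 |
| 21 | 5 | 53.6% | 48.1% | 5.5 |
| 23 | 0 | 44.6% | 39.7% | 4.9 |
| 23 | 5 | 53.2% | 48.3% | 5.0 |

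For m from 0 to 10 and SD 19–23 the gap is 4.9 to 6.0 points. A simulation with grid scores, normal-regression imputation and the 0/100 clip agrees (SD 21: 5.3–5.5).

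**Dependence on unchanged scores.** The rounded-normal model fixes the share with exactly zero change at about 12–13% in the simulation below. Assumed set-up: baseline N(48, 20), slope 0.55, residual SD 17.5, mean shift 0 or 5, 1,000,000 participants, with an added share who simply repeat their baseline score:

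| Unchanged | Observed minus imputed |
|---|---|
| 12–13% | 5.6 to 6.0 points |
| about 21% | 1.6 to 1.9 |
| about 26% | about 0 (37.1% v 37.0%; 45.6% v 46.0%) |
| about 30% | reversed (43.0% v 45.2% at mean shift 5) |

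**Candidate repairs in the same settings.** Rounding imputed scores to the 6.25 grid closes the gap when there are no added repeaters. With 21–30% unchanged it overstates response by roughly 4–9 points (at about 26% unchanged and mean shift 5: 52.3% v 45.6% observed). Predictive mean matching stayed within about 2 points of the observed rate throughout.

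**Effect by arm, taking a gap of 5.5 points and assumed imputed shares.** Arm-level distortion = gap × share: 10% gives 0.55 points, 20% gives 1.1, 30% gives 1.65. Shift in the treatment difference: 0 with equal shares, 0.55 for 10% v 20%, 1.1 for 10% v 30%. The SE of a difference in proportions at 300 per arm is about √(2 × 0.25/300) = 4.1 points.

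**The case against.** The strongest objection is that neither the size nor the sign of the gap is settled by the documents. The 5–6 point figure needs the observed score to behave like a rounded normal, and a patient-reported scale may well have more unchanged answers than that model allows. This stands, and the figure is stated as conditional for that reason.

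The effect on the comparison is also small. Both arms are affected, equal imputed shares cancel, and half a point to one point is well below the standard error. The only missingness figure is up to 10% withdrawal before Week 24 (protocol 10.2.1), and protocol Section 5.4 expects few drop-outs for lack of effect. This stands too, although the imputed share can exceed withdrawals because off-treatment scores are also replaced.

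The SAP does not name the FCS regression type, so predictive mean matching may have been intended, which would largely remove the problem. Against that, clipping at 0 and 100 is needed only if draws can leave the scale. Finally, the maximum data recovery scoring in SAP 10.6.5 lets a partly answered form fall off the 6.25 grid, so the argument holds for complete forms.

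A reader might infer that the daprodustat advantage is inflated, or that type I error rises. The documents support neither. They give no imputed share by arm, and this endpoint carries no controlled alpha.

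**Conclusion.** The inconsistency is real and follows from the SAP's own rules: one cut, two effective criteria. At the protocol's SDs of 19–23, an imputed participant is about 5–6 percentage points less likely to be called a responder, provided observed scores behave like a rounded normal. The gap is close to zero if about a quarter of participants have unchanged scores, and it reverses beyond that. A gap of 7 points would need an SD of change near 16, below the protocol's range.

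The responder percentage in each arm is distorted in proportion to its imputed share. The treatment difference moves by about 0.5–1 point for a 10–20 point imbalance in that share; the imbalance is an assumption. The primary and principal secondary conclusions are untouched, including the Vitality mean-change ANCOVA. This is a cheap improvement to a nominal endpoint.

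**What to change.** Add one sentence to SAP Section 7.3.2.1: for the Vitality responder endpoint, missing scores are imputed by FCS predictive mean matching (FCS REGPMM in PROC MI), so that every imputed Vitality score is drawn from observed scale values. Leave the imputations for the ANCOVA in Section 7.2.5.2 as planned. If predictive mean matching was already intended there, say so.

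Do not rely on rounding imputed scores to the nearest 6.25. It works only under the rounded-normal model and can overstate response when many scores are unchanged.

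The cost is one extra imputation run and its programming check.

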Section 2: Schedule of Activities, Table 1	Edited footnote #15 to add necessary ultrasound assessments for ADPKD participants at end of treatment	All participants with ADPKD will require an ultrasound within one month of study treatment discontinuation or as soon as clinically feasible as mandated by Dear Investigator Letter (DIL, dated 14 Dec 2018)
Section 2: Schedule of Activities for Patient Reported Outcomes and Actigraphy,	Added row to conduct assessment regarding healthcare resource utilization	Clarified timepoints for collection of the healthcare resource utilization data for all

Section# and Name	Description of Change	Brief Rationale
Table 2 and Schedule of Activities for Participants Permanently Discontinuing Study Treatment, Table 3	reported by participants at each visit starting with Day 1 (randomization visit) and after study treatment discontinuation	participants in the study.
Section 2: Schedule of Activities for Participants Permanently Discontinuing Study Treatment, Table 3	Added renal ultrasound for ADPKD participants upon discontinuation of study treatment.	Per the DIL, renal ultrasound is mandated for all participants with history of ADPKD who have discontinued study treatment.
Section 3.3.1 Risk Assessment	Updated risk assessment table with language related to Investigator Brochure update.	Edited Risk Assessment information to align with version 10 of the Investigator's Brochure.
Section 4. Objectives and Endpoints	Added secondary and exploratory endpoints and objectives related to BP exacerbations and concomitant medications	New objectives and endpoints were added to evaluate the effect of study treatment on BP.
Section 4. Objectives and Endpoints	Revised secondary endpoints for work productivity and regular daily activity impairment to quantify participant employment status and remove mean hours captured on WPAI-ANS-CPV	Endpoints were revised to align with the type of data captured in WPAI-ANS-CPV questionnaire.
Section 4. Objectives and Endpoints	Amended exploratory objectives for Hgb change to evaluate participants achieving a Hgb increase of $\geq 1.0\text{g/dL}$ instead of $\geq 1.2\text{g/dL}$	Exploratory objective amended to fix the administrative error (typo) from the initial protocol.
Section 4. Objectives and Endpoints	Updated the exploratory objective to capture time to first rhEPO and Transfusion use.	Objective and endpoints were updated to additionally analyse the use of rhEPO and Transfusion in the study.

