Section 6.1 Inclusion Criteria #5	Edited inclusion criterion #5 to provide clarity for requirements of compliance with oral iron	Inclusion criterion to provide further clarity on appropriate compliance with type and dose

Section# and Name	Description of Change	Brief Rationale
	dosing prior to Day 1, and removed the need for stable iron dose prior to screening.	of oral iron prior to randomization.
Section 6.2 Exclusion Criteria #13	Edited exclusion criterion #13 edited to include use of investigational device	Broadened exclusion to include participation in a study with an investigational agent or device
Section 6.2 Exclusion Criteria #22	Added exclusion criterion #22 for uncontrolled hypertension	Additional criterion added to exclude participants with uncontrolled hypertension as worsening of hypertension has been added to the list of AESI for daprodustat per IB Version 10
Table 6. Study Treatment Dosing Algorithm	Instructions to repeat and average HemoCue Hgb assessment for Hgb <8.5 g/dL	Language added to align with the IRT system programming.
Section 8.1 Discontinuation of Study Treatment	Added information regarding discontinuation of study treatment in participants with ADPKD.	Study treatment must be discontinued in participants with ADPKD who experience greater than expected worsening of kidney function and/or cyst enlargement with no other cause or clinical scenario identified.
Section 8.2 Withdrawal from the Study	Added language related to alternative methods of follow-up	To align with the ICF and provide information regarding additional methods of follow-up for participants unwilling to perform study clinic visits.
Section 8.3 Lost to Follow Up	Added language regarding alternative methods of follow-up for participants potentially lost to follow up.	To provide further guidance on evaluation of participant status after the participant is lost to follow up.
Section 9.1 Screening and Critical Baseline Assessments	Added language regarding retests with a new blood sample and entering HemoCue Hgb values into the IRT system	To ensure sites they may retest Hgb with a new blood sample for the day 1 visit. Additional clarification provided regarding data entry criteria to capture HemoCue Hgb values

Section# and Name	Description of Change	Brief Rationale
		in the IRT system.

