Potential Risk of Clinical Significance	Summary of Data/Rationale for Risk	Mitigation Strategy
	
receiving daprodustat vs. 66/135 (49%) for rhEPO.
 
The data received to date from completed clinical trials with daprodustat are insufficient to refute this risk.
	

Death, MI, stroke, heart failure, thromboembolic events, thrombosis of vascular access at Hgb levels which are within the normal range (i.e. not polycythemic conditions)
	
Marketed rhEPO/ Erythropoetin-stimulating agent (ESAs) have been associated with an increased risk for death and serious cardiovascular events when used in patients with anemia of CKD. Clinical studies with marketed rhEPO/analogs have suggested "higher" target hemoglobin, rate of hemoglobin rise of greater than 1 g/dL in any 2-week period, and/or higher doses may contribute to these risks.
 
In non-clinical studies conducted to date, not observed at tolerated doses when hemoglobin/hematocrit within normal range for species.
 
Integrated AE data from clinical trials with daprodustat [including 2 global phase 2b studies (24-week treatment duration) and 2 Japanese phase 3 studies (52-week treatment duration)]: No meaningful difference was seen between treatment groups in the overall incidence of this AESI: [39/688 (5.5%) daprodustat vs. 25/404 (6%) rhEPO; 0.92 relative risk (95% confidence interval: 0.55, 1.53)]. Within this composite AESI, the most frequent event types were heart failure (at least 12 events daprodustat vs. at least 13 events rhEPO) and thrombosis (at least 14 events daprodustat vs. at least 8 event rhEPO); and a numerical imbalance was noted in events of myocardial ischemia (at least 7 events daprodustat vs. at least 1 event rhEPO). The small number of events makes it difficult to draw any firm conclusions.
 
The clinical data received to date from completed clinical trials with daprodustat are insufficient to substantiate or refute this risk.
	
 • Specific eligibility criteria related to CV risk are outlined in Section 6.2. • Hgb will be closely monitored throughout the dosing period as outlined in the SoA (Section 2). • Instream monitoring of safety data by internal safety review team.

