9.3.7. Adverse Events of Special Interest

The investigator or site staff will be responsible for detecting, documenting and reporting any events that may represent the AEs of special interest listed below (using preferred terms):

- Death, MI, stroke, heart failure, thromboembolic events, thrombosis of vascular access
- Thrombosis and/or tissue ischemia secondary to excessive erythropoiesis
- Worsening of hypertension
- Cardiomyopathy
- Pulmonary artery hypertension (see also Section 9.3.2)
- Cancer-related mortality or tumor progression and recurrence
- Esophageal and gastric erosions
- Proliferative retinopathy, macular edema, choroidal neovascularization
- Exacerbation of rheumatoid arthritis

The Death CRF is provided immediately after the occurrence or outcome of death is reported. Initial and follow-up reports regarding death must be completed within one week of when the death is reported.

The results of any investigation regarding adverse events of special interest should be recorded in the relevant sections of the participant's eCRF.

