| 
arms. The models will be fitted to BP (SBP, DBP, and MAP) data collected after baseline up to Week 28. All available on-treatment BP (SBP, DBP, and MAP) data will be used in the model; a subject must have a baseline value and at least one on-treatment assessment to be included in the analysis. The models will include factors for treatment, time, region (see Section 5.3), baseline BP (SBP, DBP, and MAP) and the baseline BP (SBP, DBP, and MAP) by time and treatment by time interaction terms. Analyses will be done with the MIXED procedure in SAS, using the Kenward-Roger option to estimate denominator degrees of freedom and standard errors.
 
 For the % of participants with at least one BP exacerbation event during the study, a Cochran-Mantel-Haenszel (CMH) chi-squared test, adjusting for treatment and region (see Section 5.3), will be used to make comparisons between the treatment groups. At least one BP exacerbation is defined in Section 10.6.3. |
| 
Model Results Presentation
 
 For the MMRM analyses of change from baseline in BP (SBP, DBP, and MAP) data, an LSMEANS statement will provide adjusted treatment group means and standard errors and a point estimate and two-sided 95% confidence interval for the adjusted mean treatment difference (daprodustat - placebo) and a one-sided superiority p-value for this test at Week 28 for the BP (SBP, DBP, and MAP) data. The number and % of participants with at least one BP exacerbation event during the study, by treatment group, relative response rate (daprodustat vs. placebo) and two-sided 95% CI will be provided along with the one-sided CMH p-value for the treatment group comparison. |
| 
Model Results Interpretation
 
 One-sided p-values will be compared to 0.025 to assess nominal significance |

HRQoL and Utility Score: Additional SF-36 Analyses

| |
|--|
| 
Secondary Efficacy Statistical Analyses: SF-36 Vitality
 |
| 
Endpoint / Variables
 
 Mean Change in SF-36 Vitality domain between baseline and Week 28, utilizing TREAT historical control data |

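### The BP endpoints are judged by a one-sided p-value with no stated direction, so the only stated rule either cannot flag a BP rise on daprodustat or would label it superiority

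*SAP*

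**What the plan says.** SAP 7.3.2.1, Blood Pressure, fits a mixed model to on-treatment SBP, DBP and MAP. At Week 28 it reports the model-based difference between the arms (daprodustat minus placebo) with its two-sided 95% interval. The same sentence then adds the test: "and a one-sided superiority p-value for this test at Week 28 for the BP (SBP, DBP, and MAP) data". For participants with at least one BP exacerbation it gives a daprodustat-to-placebo ratio with a two-sided 95% interval, "along with the one-sided CMH p-value for the treatment group comparison". The interpretation paragraph is a single line: "One-sided p-values will be compared to 0.025 to assess nominal significance".

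The objective in Protocol Section 4 and SAP 2.2 is a neutral comparison of the arms on BP. The amendment table gives the reason for it as "New objectives and endpoints were added to evaluate the effect of study treatment on BP". Protocol 9.3.7 lists "Worsening of hypertension" as an adverse event of special interest (AESI). On that risk, Protocol 3.3.1 concludes: "The data received to date from completed clinical trials with daprodustat are insufficient to refute this risk". The same amendment justifies exclusion criterion 22 on the ground that "worsening of hypertension has been added to the list of AESI for daprodustat per IB Version 10".

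SAP 5.5 places these endpoints outside the testing hierarchy, unadjusted, with nominal one-sided 2.5% levels. SAP 10.6.1 allows two-sided p-values to be produced after the study if a publication needs them.

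**The concern.** The BP section follows the layout used for the efficacy endpoints, including reporting exacerbations as a relative response rate. For hemoglobin that layout works, because benefit has one direction and the SAP states it: under Hgb Variability in the same section, superiority in the mixed-model analysis needs the lower 95% limit above 0 and a one-sided p below 0.025. The BP section gives neither a direction nor a rule for reading the interval.

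A BP exacerbation is defined in SAP 10.6.3 by a rise from baseline or a high absolute value, so it is an unfavourable event. A one-sided test of a quantity that matters in both directions has to ignore one of them. Here the SAP does not say which. At stake is how a difference in measured BP would be labelled under the prespecified rule. This section is the only between-arm inferential analysis of measured BP in the plan.

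**Working it through.** **Plan's own figure.** The documents give no SD, effect size or power for BP, so there is no BP figure to reproduce. The one-sided 2.5% convention can be checked on SF-36 vitality (Protocol 10.2.1: difference 5, SD 21, 270 per arm). SE = 21 × √(2/270) = 1.807 and 5/1.807 = 2.766, so power = Φ(2.766 − 1.960) = 0.790. This matches the stated 79%.

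**Inputs for BP.** The 270 per arm is the planned evaluable number (Protocol 10.2.1). I also use 200, because the BP model takes on-treatment values only. An SD of 15 to 20 mmHg and an observed difference (daprodustat minus placebo) of +3 to +5 mmHg are assumptions.

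**Formulas** (normal approximation), with d the observed difference:
- SE = SD × √(2/n) and z = d/SE
- p if superiority means lower BP: Φ(z)
- p if superiority means a difference above 0: 1 − Φ(z)
- two-sided p: 2 × (1 − Φ(z)) for d > 0
- 95% interval: d ± 1.96 × SE

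**Central case:** d = +4, SD = 18, n = 270. SE = 18 × √(2/270) = 1.549 and z = 2.58.
- Lower BP counted as superior: p = 0.995
- Difference above 0 counted as superior: p = 0.005
- Two-sided p = 0.010
- 95% interval: 0.96 to 7.04

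**Range:**

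| d (mmHg) | SD | n per arm | p, lower BP superior | p, difference > 0 | two-sided p | 95% interval |
|---|---|---|---|---|---|---|
| +3 | 20 | 200 | 0.933 | 0.067 | 0.134 | −0.92 to 6.92 |
| +3 | 15 | 270 | 0.990 | 0.010 | 0.020 | 0.47 to 5.53 |
| +4 | 18 | 270 | 0.995 | 0.005 | 0.010 | 0.96 to 7.04 |
| +5 | 20 | 200 | 0.994 | 0.006 | 0.012 | 1.08 to 8.92 |
| +5 | 15 | 270 | 0.9999 | 0.0001 | 0.0001 | 2.47 to 7.53 |

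I combined SD 15, 18 and 20, d = 3, 4 and 5, and n = 200 and 270, which gives 18 cases. The interval excludes 0 in 14 of them, including every case with d of 4 or more. The p-value for lower BP is at least 0.93 in all 18.

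The first reading does not depend on the assumptions: if d > 0 then z > 0, so Φ(z) > 0.5 and the 0.025 threshold cannot be met.

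**Exacerbations.** A CMH chi-squared statistic carries no sign, so a one-sided p-value exists only once a direction is chosen. The section chooses none, and here it does not even use the word superiority.

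**The case against.** The strongest reply is that nothing is hidden. The sentence that plans the one-sided p-value also plans a two-sided 95% interval. For the mean differences, a lower limit above 0 is equivalent to a one-sided p below 0.025 for a rise. A one-sided p of 0.995 converts directly to a two-sided 0.010, and SAP 10.6.1 provides for two-sided p-values if a publication needs them. No decision rests on the BP p-values, and the SAP nowhere says that a non-significant result means no harm.

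Harm is also examined elsewhere:
- AESI tables with exposure-adjusted rates, and a dedicated table for worsening hypertension (3.16, 3.55)
- relative risks with 95% intervals for adverse event terms (SAP 8.2, 10.6.4)
- vital-sign summaries and values of potential clinical importance (3.33-3.35)
- changes in BP medication (2.126)

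All of this stands, and it rules out some stronger readings. A reader might infer that a BP rise could go unseen or could never be called significant. The planned intervals contradict that. A reader might infer that the endpoints were added because hypertension is a suspected harm. The amendment and the AESI listing make that plausible, but the stated reason is neutral, and the AESI rationale is attached to exclusion criterion 22 and the AESI list. A reader might also take the SAP to define superiority as lower BP. That is the natural reading, but it is not written down.

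The reply does not repair the rule. The other summaries either describe measured BP without comparing the arms inferentially or concern reported events. A p-value produced later for publication is not a prespecified interpretation.

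**Conclusion.** The point holds as a defect in the p-value and its interpretation rule. The direction of superiority for BP is undefined. If it means lower BP, any observed rise gives p above 0.5 and cannot meet the rule. If the hemoglobin convention were carried over, a rise of +4 mmHg (SD 18, 270 per arm) would give p = 0.005 and be labelled superiority. In both cases the point estimate and the interval of 0.96 to 7.04 are unchanged, so no estimate is biased and no confirmatory conclusion is touched.

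The size of the p-values rests on an assumed SD and difference. The conclusion about the rule needs neither. It is worth correcting before unblinding, because the objective is neutral and worsening hypertension is an AESI that the sponsor regards as not refuted.

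**What to change.** In SAP 7.3.2.1, Blood Pressure, and Tables 2.72-2.75, replace the one-sided p-values with two-sided ones for SBP, DBP, MAP and BP exacerbation. Replace the interpretation line with a rule in both directions:

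- A 95% interval for daprodustat minus placebo wholly above 0, or for the exacerbation ratio wholly above 1, is nominal evidence of higher BP or more exacerbations on daprodustat.
- An interval wholly below 0, or below 1 for the ratio, is nominal evidence of lower BP or fewer exacerbations.

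Name the method for the ratio's interval, since the section gives none and the interval and the CMH test may disagree near the boundary. Add an exception for BP to the one-sided nominal level in SAP 5.5. Record the change in SAP Table 1, because Protocol 10.4.3 carries the same one-sided wording.

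The cost is SAP wording and small edits to the table shells. No extra data are needed. The endpoints lie outside the multiplicity hierarchy, so no alpha is affected.
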